**Protocol Revision History**

Initial Approval Version	08/28/15
Amendment #1 Version	12/22/15
Amendment #2 Version	06/21/16
Amendment #3 Version	10/17/16
Amendment #4 Version	12/22/16
Amendment #5 Version	06/26/17
Amendment #6 Version	08/01/17
Amendment #7 Version	01/26/18
Amendment #8 Version	10/04/18
Amendment #9 Version	02/04/19
Amendment #10 Version	11/01/19

**A Non-Inferiority Study of Doxorubicin with Upfront Dexrazoxane for the Treatment of Advanced or Metastatic Soft Tissue Sarcoma**

**Study Schema**

## **Glossary of Abbreviations**

AE	Adverse event
ALT (SGPT)	Alanine transaminase (serum glutamate pyruvic transaminase)
AST (SGOT)	Aspartate transaminase (serum glutamic oxaloacetic transaminase)
B-HCG	Beta human chorionic gonadotropin
BNP	B-type natriuretic peptide
CBC	Complete blood count
CMP	Complete metabolic panel
CR	Complete response
CRF	Case report form
CT	Computed tomography
CTCAE	Common Terminology Criteria for Adverse Events
CTEP	Cancer Therapy Evaluation Program
DNA	deoxyribonucleic acid
DSM	Data and Safety Monitoring
ECOG	Eastern Cooperative Oncology Group
EDTA	ethylenediaminetetraacetic acid
EORTC	European Organisation for Research and Treatment of Cancer
FDA	Food and Drug Administration
HIV	Human Immunodeficiency Virus
HRPO	Human Research Protection Office (IRB)
HRV	Heart rate variability
IRB	Institutional Review Board
IULN	Institutional upper limit of normal
LIIF	Load independent index of filling
LVEF	Left ventricular ejection fraction
MRI	Magnetic resonance imaging
NCI	National Cancer Institute
OHRP	Office of Human Research Protections
OS	Overall survival
PD	Progressive disease
PFS	Progression-free survival
PI	Principal investigator
PR	Partial response
QASMC	Quality Assurance and Safety Monitoring Committee
RECIST	Response Evaluation Criteria in Solid Tumors (Committee)
RNA	Ribonucleic acid
RR	Response rate
SAE	Serious adverse event
SD	Stable disease
UPN	Unique patient number

### **1.2 Treatment of Metastatic Sarcoma**

Generally, localized sarcoma is treated with surgery when feasible and adjuvant radiation with or without chemotherapy. Like any other cancer, sarcomas have the ability for hematogenous spread to develop distant metastases. For the majority of patients with metastatic soft tissue sarcoma, their cancer is incurable. Therefore, the goal of treatment is to reduce cancer bulk, minimize cancer related symptoms, improve quality of life, and increase overall survival. Despite our best efforts, the median survival of patients with distant metastases is 11 to 15 months with approximately 20-25% of patients being alive at three years .

Most cases of advanced soft tissue sarcoma are treated with conventional chemotherapy for palliation. A common treatment regimen is single agent doxorubicin. There have been many attempts to improve upon this treatment approach with dose intensification and combination therapies. A randomized trial by EORTC Soft Tissue and Bone Sarcoma Group compared doxorubicin alone, doxorubicin plus ifosfamide, and a four-drug regimen of cyclophosphamide, vincristine, doxorubicin, and dacarbazine. The combination treatment did not significantly improve overall survival (OS), progression-free survival (PFS), or response rate (RR), and these combination regimens were significantly more toxic . Another randomized phase III trial evaluated single agent doxorubicin compared to doxorubicin plus ifosfamide in advanced or metastatic soft tissue sarcoma. There was no significant difference in OS between the two treatment groups (median OS 12.8 months vs. 14.3 months, p=0.076). The combination chemotherapy group had a significantly higher PFS (7.4 months vs. 4.6 months, p 0.003) and there was a higher overall response rate in the combination treatment arm (26% vs. 14%) .

### **1.3 Anthracyclines**

Doxorubicin is a commonly used chemotherapy classified as an anthracycline. It is a natural product of a fungus, *Streptomyces peucetius* var. *caseius*, with antitumor properties. Anthracyclines have a tetracyclic ring structure attaches to a sugar and have quinone and hydroquinone moieties on adjacent rings that permit the gain and loss of electrons.

Anthracyclines have several mechanisms of antitumor activity. They bind to DNA through intercalation to block the synthesis of DNA and RNA. This leads to DNA strand scission. Another mechanism of cytotoxicity includes inhibiting topoisomerase II, resulting in impaired DNA repair. Other major cellular enzymes affected by anthracyclines include DNA and RNA polymerase. Another mechanism of cellular destruction is the generation of semiquinone free radicals and oxygen-free radical through an iron-dependent reductive process. The presence of quinone group is to allow free radical to form and accumulate in normal and malignant cells. These free radicals will not only damage malignant cells but is also thought to contribute to toxicity of normal tissue .

### **1.3.1 Cardiotoxicity and Anthracyclines**

The most concerning toxicity of anthracyclines is cardiotoxicity. Anthracycline-induced cardiotoxicity ranges from subclinical left ventricular dysfunction to severe cardiomyopathy with heart failure. Cardiotoxicity may occur acutely within the first week of treatment, early within one year of completing therapy, or late after one year of completing anthracycline treatment.

The cardiotoxic effects of doxorubicin have been well established in studies dating back decades . The estimated incidence of heart failure for patients on doxorubicin receiving a cumulative dose of 400-550 mg/m^2 range widely from a relatively low 3-7% by Von Hoff et al 1979 to a significantly higher 27% by Speyer et al 1992. At higher doses around 1000 mg/m^2 as many as half of patients may experience the cardiotoxic effects .

The exact mechanism of anthracycline-induced cardiotoxicity is not entirely known. It has traditionally been believed that the cardiotoxic effects of have been mediated by redox cycling and the generation of reactive oxygen species; newer evidence suggests that it may be specifically mediated by topoisomerase-IIβ in cardiac myocytes . An additional mechanism may include accumulation of mitochondrial iron leading to increased reactive oxygen species inside the cardiac myocyte .

### **1.4 Dexrazoxane (Zinecard)**

Dexrazoxane is a derivative of ethylenediaminetetraacetic acid (EDTA) and acts as a free-radical scavenger. It chelates iron, reducing anthracycline-metal iron complexes and thus the formation of superoxide radicals . It has been shown to drastically reduce the incidence of anthracycline-induced cardiomyopathy in breast cancer  and sarcoma . The use of dexrazoxane has gained widespread currency and is now considered standard of care in several treatment regimens for sarcoma and breast cancer.

The effect of dexrazoxane on the efficacy of the chemotherapy regimen remains a topic of debate. Some studies of breast cancer patients undergoing the a multi-agent chemotherapy regimen known as FAC (a combination of 5-fluorouracil, doxorubicin, and

cyclophosphamide) have shown lower response rates in patients receiving dextrazoxane , prompting the FDA to limit its labeling to patients who have already received a cumulative dose of doxorubicin of  $300 \text{ mg/m}^2$ . However, others have demonstrated no difference , and while a recent Cochrane review by Val Dalen et al have shown a non-significant trend towards decreased RR ( $p=0.08$ ) there was virtually no difference in PFS ( $p=0.89$ ) or OS ( $p=0.65$ ) . Furthermore, other studies suggest that dextrazoxane may actually limit the development of resistance  and allow patients to receive greater total doses of doxorubicin . This has led some  to propose the initiation of dextrazoxane at doses of doxorubicin as low as  $150 \text{ mg/m}^2$ . Nonetheless this has not been adopted by any of the major guideline writing groups.

The overwhelming majority of these trials have been conducted in breast cancer patients, and there is little evidence either for or against its early use in sarcoma patients. Moreover, in most of the breast cancer trials, coadministration of doxorubicin and dextrazoxane with cyclophosphamide and 5-fluorouracil is common, creating a possible confounder not present in standard sarcoma regimens. As such, clinical trials are needed comparing the outcomes of early versus late administration of dextrazoxane in sarcoma patients.

## 1.5 Measurement of Cardiac Toxicity

### 1.5.1 Decrease in Left Ventricular Ejection Fraction

The use of echocardiography to measure left ventricular dysfunction is an evolving science. Currently the ejection fraction, measured on a 2D echocardiogram using echogenic contrast is commonly used to monitor cardiotoxicity. However, the interoperator variability is wide and the ejection fraction actually measures a late deterioration of LV function. In most cases of anthracycline cardiotoxicity, there are permanent changes in the myocardium structure before it is reflected in a reduced ejection fraction.

There are three commonly used modalities for the measurement of left ventricular (LV) function by echocardiography, the modified Simpson's biplane method, strain measures, and 3D echocardiography. Of these, the oldest and most widely used is the Simpson's biplane estimate. This method relies on the areas of elliptical discs drawn on the apical four chamber and apical two chamber views. The difference between the end-diastolic and end-systolic volumes is then used to calculate the ejection fraction. However, this method is imperfect and does not account for changes such as left ventricular hypertrophy which may see paradoxically elevated ejection fractions even in the presence of significant systolic dysfunction.

In single center studies, calculating the ejection fraction using 3D echocardiography has been recommended to be a more consistent measure of LV function. 3D echocardiography has been around for decades, but only recently have advances in technology made this modality available for routine clinical use . Several studies have demonstrated improved accuracy and reproducibility of ejection fractions calculated by the 3D echo compared to the traditional Simpson's

biplane method 14, 27, 28. However, owing to its widespread use and common acceptance use as a standard measurement in most facilities, we propose a primary endpoint of LVEF by the modified Simpson's biplane method.

A more recently developed method measures left ventricular strain, strain rate, and peak myocardial velocity 29, 30, 31. This method uses 2D echocardiography to evaluate the degree of shortening of the ventricular myocardium using the apical 2-, 3- and 4- chamber views. A recent systematic review by Thavendiranathan et al showed the efficacy of stain measurements as an early marker of LV dysfunction in patients undergoing anthracycline-based chemotherapy 32.

Left ventricular diastolic dysfunction is a relatively recently identified clinical entity affecting nearly half of all patients with cardiac dysfunction. It is characterized by abnormal relaxation of the ventricle even in the presence of a preserved ejection fraction. Traditional methods of measuring diastolic function, including mitral inflow pulsed wave Doppler and pulmonary vein Doppler, are classified as load dependent, meaning that the measurements are dependent on and will vary with the filling pressure of the heart. More recently developed methods, including tissue Doppler imaging of the mitral annulus and color M-mode, are independent of this parameter and may vary less based on patient's fluid status. These parameters will be measured and evaluated against the Ejection fraction endpoint again to determine if changes in diastolic function will be an early marker of depressed ejection fraction.

In order to quality control these measurements, carried out in our clinical echocardiographic laboratory, the echocardiographic images will be also evaluated in our core echocardiographic laboratory. The clinical decisions will be based on the clinically obtained echocardiograms in consultation with a cardio-oncologist

A separate measure of diastolic function, Load Independent Index of Filling, has been developed at Washington University 33, 34. This can be measured using a standard echocardiogram. We propose measuring this parameter on all echocardiograms obtained during the study and evaluating whether changes in the LIIF can be an early marker of LV systolic dysfunction.

These more recent echogenic measures of LV function will be monitored to determine if they can predict LV deterioration as measured on the ejection fraction.

### **1.5.2 Biomarkers as Measures of Cardiotoxicity**

Serum B-type natriuretic peptide (BNP), an endogenous hormone released in response to increased preload is established as a surrogate maker for heart failure 35, 36.

Cardiac troponin I, a cardiac myocyte protein and a marker for cardiac damage has long been used as marker for coronary ischemia 37, 38. A more recently developed

high sensitivity troponin I assay has the potential to reveal myocardial damage at a lower threshold than the current clinically used troponin. It may also have the potential to detect patients at risk for developing cardiotoxicity long before it is manifested as a decrease in left ventricular ejection fraction on echocardiography.

Galectin-3 (Gal-3), a soluble B-galactosidase-binding lectin, is produced by activated macrophages and induces cardiac fibroblasts to deposit type 1 collagen. Galectin-3 production is increased prior to and after the onset of heart failure (HF) and is believed to play a role in cardiac fibrosis. Several studies have shown that elevated Galectin-3 serum concentrations are associated with an increased two year risk of HF following acute coronary syndrome, cumulative ten year incidence of HF in the Framingham Offspring Cohort, and 18 month survival among HF patients.

Heart rate variability (HRV) is well known to provide information about the autonomic status of a patient, segregating patients with excessive sympathetic tone from those with excessive vagal tone . A reduced HRV has been shown to be correlated to autonomic dysfunction and increased overall mortality . It has also been used for prognostic purposes in some cancers .

### **1.6 Amendment #3 – Addition of Olaratumab**

In October 2016, olaratumab (Lartruvo) was approved by the FDA to be given in combination with doxorubicin for the treatment of soft tissue sarcomas with a histologic subtype for which an anthracycline-containing regimen is appropriate and which is not amenable to curative treatment with radiotherapy or surgery. Amendment #3 was made to the protocol to allow patients to receive this new standard of care treatment.

### **1.7 Amendment #9—Removal of Olaratumab**

In January 2019 Eli Lilly and Company reported that the results of the Phase 3 study of olaratumab (Lartruvo), in combination with doxorubicin in patients with advanced or metastatic soft tissue sarcoma, did not confirm the clinical benefit of olaratumab in combination with doxorubicin as compared to doxorubicin alone. Therefore olaratumab is being removed from the front line standard of care regimen. Amendment #9 was made to the protocol to reflect these changes to the standard of care treatment. Section 9.1 was also updated to clarify 9.1 the evaluation of cardiac function using echocardiogram and the addition of 10 sarcoma banking protocol #201203042 participants to be used as controls in the secondary objectives analysis.

## **2.0 OBJECTIVES**

### **2.1 Primary Objective**

To determine progression-free survival (PFS) in patients with metastatic soft tissue sarcoma who are treated with doxorubicin in combination with dextrazoxane.

## **2.2 Secondary Objectives**

1. To determine cardiac-related mortality in patients with metastatic soft tissue sarcoma who are treated with doxorubicin in combination with dextrazoxane.
2. To determine incidence of heart failure or cardiomyopathy in patients with metastatic soft tissue sarcoma who are treated with doxorubicin in combination with dextrazoxane.
3. To evaluate additional echocardiogram parameters of left ventricular ejection fraction to determine if either 3D echocardiogram or ventricular strain is able to serve as an early marker of cardiac dysfunction compared to 2d echocardiogram modified Simpson's biplane method of LVEF.

## **3.0 PATIENT SELECTION**

At least 57 but up to 65 patients will be enrolled in this study to receive dextrazoxane concurrently with standard of care doxorubicin. At the completion of accrual, an additional 10 patients meeting the eligibility criteria below will be enrolled as a control group for the correlative studies as there is no baseline data for these tests; these patients will receive institutional standard of care therapy.

### **3.1 Inclusion Criteria**

1. Histologically confirmed grade 2 or 3 soft tissue sarcoma that is unresectable or metastatic. Surgery for primary or metastatic disease after chemotherapy following a response is allowed. Patients with the following tumor types are eligible:
  - a. Undifferentiated pleomorphic sarcoma
  - b. Leiomyosarcoma
  - c. Malignant fibrous histiocytoma
  - d. Liposarcoma (myxoid/round cell, pleomorphic or dedifferentiated)
  - e. Synovial sarcoma
  - f. Myxofibrosarcoma
  - g. Angiosarcoma
  - h. Fibrosarcoma
  - i. Malignant peripheral nerve sheath tumor
  - j. Epithelioid sarcoma
  - k. Unclassified high-grade sarcoma (not otherwise specified)
  - l. Soft tissue sarcoma for which treatment with an anthracycline is appropriate at the approval of the PI
2. Measurable disease according to RECIST 1.1; that is, measurable disease defined as lesions that can be accurately measured in at least one dimension (longest diameter to

be recorded) as  $\geq 10$  mm with CT scan, as  $\geq 20$  mm by chest x-ray, or  $\geq 10$  mm with calipers by clinical exam.

3. Planning to initiate treatment with doxorubicin (starting dose of  $75 \text{ mg/m}^2$ ) as routine care.
4. Prior adjuvant chemotherapy with gemcitabine and/or docetaxel/paclitaxel is allowed.
5. At least 18 years of age.
6. ECOG performance status of 0 or 1 (see Appendix A).
7. Adequate organ function defined as:
  - a. Leukocytes  $\geq 3,000/\text{mcL}$
  - b. Absolute neutrophil count  $\geq 1,500/\text{mcL}$
  - c. Platelets  $\geq 100,000/\text{mcL}$
  - d. Total bilirubin  $\leq 1.5 \times \text{IULN}$
  - e. AST(SGOT)/ALT(SGPT)  $\leq 3.0 \times \text{IULN}$
  - f. Creatinine  $\leq \text{IULN}$  OR creatinine clearance  $\geq 60 \text{ mL/min}/1.73 \text{ m}^2$  for patients with creatinine levels above institutional normal. Creatinine clearance should be calculated using the actual weight from day 1 of the cycle
8. Women of childbearing potential and men must agree to use adequate contraception (hormonal or barrier method of birth control, abstinence) prior to study entry and for the duration of study participation. Should a woman become pregnant or suspect she is pregnant while participating in this study, she must inform her treating physician immediately.
9. Able to understand and willing to sign an IRB approved written informed consent document (or that of legally authorized representative, if applicable).

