### 3.2 Exclusion Criteria

1. Myocardial infarction within the past 12 months, or stable or unstable angina.
2. Systolic heart failure defined as left ventricular ejection fraction  $\leq 45\%$ .
3. Symptomatic valvular heart disease.
4. Prior chemotherapy for advanced or metastatic disease.
5. Known brain metastases.
6. Prior or second primary malignancies within the last two years (except carcinoma in situ of the cervix, non-metastatic prostate cancer, or basal cell or squamous cell carcinoma of the skin which were treated with local resection only; prior adjuvant androgen deprivation therapy in the case of prostate cancer is permitted, but current adjuvant androgen deprivation therapy is not).
7. Currently receiving any investigational agents.
8. A history of allergic reactions attributed to compounds of similar chemical or biologic composition to dextrazoxane or other agents used in the study.
9. Uncontrolled intercurrent illness including, but not limited to, ongoing or active infection, symptomatic congestive heart failure, or psychiatric illness/social situations that would limit compliance with study requirements.
10. Pregnant and/or breastfeeding. Patient must have a negative pregnancy test within 14 days of study entry.
11. Known HIV-positivity on combination antiretroviral therapy because of the potential for pharmacokinetic interactions with dextrazoxane. In addition, these patients are at

increased risk of lethal infections when treated with marrow-suppressive therapy. Appropriate studies will be undertaken in patients receiving combination antiretroviral therapy when indicated.

12. Prior treatment with anthracyclines.

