## **5.0 TREATMENT PLAN**

### **5.1 Agent Administration**

Dexrazoxane will be given intravenously on an outpatient basis over 15 minutes on each day that doxorubicin is given. Dexrazoxane should be given no more than 30 minutes prior to administration of doxorubicin, which is typically given on Day 1 of a 21-day cycle. Dosing is a 10:1 ratio of dexrazoxane to doxorubicin; doxorubicin will be started at 75 mg/m^2, so dexrazoxane dosing would be 750 mg/m^2. Doxorubicin is being given as routine care; the administration is not dictated per protocol. Patients who are enrolled in the control group will receive institutional standard of care therapy.

In the event of a national shortage of dexrazoxane, 72-hour infusional doxorubicin can be used instead of dexrazoxane and bolus doxorubicin.

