## **5.2 General Concomitant Medication and Supportive Care Guidelines**

Premedications and supportive care may be given routinely as needed to prevent or treat doxorubicin-related toxicities or adverse reactions.

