### **14.3.1 Sample Size and Statistical Power**

The historic control used for comparison is based on data published by Judson et al. Patients with advanced or metastatic soft tissue sarcoma treated with single agent doxorubicin had a median PFS of 4.6 months. We consider a median PFS of 3.7 months (safety margin of 20%) to be non-inferior to the PFS seen in patients treated with doxorubicin alone. We will be using a one-sided log-rank test at an alpha level of 0.05 with a power of 0.80 to determine if treatment of doxorubicin with upfront dextrazoxane is non-inferior to doxorubicin alone.

[figure not shown]
A maximum of 65 patients may be enrolled to allow for a 10% dropout rate, resulting in at least 57 patients for testing of the primary endpoint. Using 57 patients, we have 0.80 power at a 1-sided significance level of 0.05 to detect a median PFS 3.7 months compared to this historic control's PFS of 4.6 months.

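### The benchmark is single-agent doxorubicin, but no rule limits enrolled patients to it, so an effective add-on drug could bias the primary test toward non-inferiority

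*Combined protocol and SAP*

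**What the plan says.** **The comparator is one drug.** Section 14.3.1 takes its historical control from patients "treated with single agent doxorubicin had a median PFS of 4.6 months". It states the hypothesis as non-inferiority to doxorubicin alone, with 3.7 months as the margin.

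**The entry and treatment rules are not limited to one drug.**
- Section 3.1, inclusion 3: "Planning to initiate treatment with doxorubicin", with a 75 mg/m² starting dose, as routine care. Nothing says that it must be the only agent.
- Section 5.1: "Doxorubicin is being given as routine care; the administration is not dictated per protocol".
- Section 3.2: the nearest exclusion for concurrent drugs is number 7, "Currently receiving any investigational agents". Exclusions 4 and 12 concern earlier treatment.
- Section 5.2 covers supportive care only: "Premedications and supportive care may be given routinely as needed to prevent or treat doxorubicin-related toxicities or adverse reactions".

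**An add-on has been allowed.** Section 1.6, on olaratumab given with doxorubicin, says: "Amendment #3 was made to the protocol to allow patients to receive this new standard of care treatment". Section 1.7 describes its later removal as a change in standard of care. The current criteria contain no exclusion of concurrent anticancer drugs.

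**The analysis does not separate regimens.** Section 14.2 applies intention to treat to the dexrazoxane cohort. It has no restriction, stratification or sensitivity analysis by accompanying chemotherapy.

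**The concern.** With a fixed historical figure there is no concurrent arm in which an add-on's effect could cancel out. If some patients receive a second effective drug, their longer PFS enters the cohort estimate and is compared with a median obtained without that drug. Any loss of efficacy from upfront dexrazoxane is then partly hidden, and the error runs toward the conclusion the trial hopes to reach.

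The documents give a reason to take this seriously. The trial that supplies the 4.6 months also tested added ifosfamide, and section 1.2 reports: "The combination chemotherapy group had a significantly higher PFS (7.4 months vs. 4.6 months, p 0.003". Section 1.4 faults the breast cancer evidence for co-administered drugs, "creating a possible confounder not present in standard sarcoma regimens", but the entry rules do not secure that absence here.

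**Working it through.** **Inputs.** Benchmark 4.6 months, margin 3.7 months, one-sided alpha 0.05 and 57 patients (14.3.1); 7.4 against 4.6 months with ifosfamide added (1.2); testing by Kaplan-Meier median and 95% confidence interval (14.2). Assumed, because the documents do not say: exponential PFS, all 57 events observed, add-on share f, and the ratio r by which the add-on multiplies median PFS.

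**The plan's own power figure.** The hazard ratio at the margin is 4.6/3.7 = 1.243, with logarithm 0.2177. One-sample log-rank power is Φ(√57 × 0.2177 − 1.645) = Φ(1.644 − 1.645) = 0.50, not the stated 0.80. Power of 0.80 needs (1.645 + 0.842)² / 0.2177², about 131 events. This is a separate matter, and the point here does not depend on it.

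**Step 1: median of a mixed cohort.** Set the true single-agent median, with dexrazoxane, at 3.7 months, so that a non-inferiority claim should occur at most about 5% of the time. The largest ratio the documents support is r = 7.4/4.6 = 1.609, which gives add-on patients a median of 3.7 × 1.609 = 5.95 months. The mixed median t solves

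(1 − f) × 2^(−t/3.7) + f × 2^(−t/5.95) = 0.5.

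**Step 2: false non-inferiority.** Simulate 40,000 trials of 57 patients under two decision rules:
- Log-rank (14.3.1): O = 57 events, E = Σ tᵢ × ln 2 / 3.7, and claim if (E − O)/√E > 1.645.
- Kaplan-Meier (one reading of 14.2): claim if the lower 95% limit of the median exceeds 3.7 months (plain interval).

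Results with r = 1.609:

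| Add-on share | Mixed median (months) | Log-rank | Kaplan-Meier lower limit |
|---|---|---|---|
| 0% | 3.70 | 0.04 | 0.03 |
| 10% | 3.87 | 0.11 | 0.05 |
| 20% | 4.04 | 0.21 | 0.08 |
| 30% | 4.23 | 0.34 | 0.12 |

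**Step 3: weaker add-ons.** With r = 1.25, the log-rank rates at 10%, 20% and 30% are 0.06, 0.09 and 0.12. With r = 1 the rate stays at about 0.04 at every share.

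**Step 4: share needed to hide the whole margin.** If every patient has lost 20%, so that add-on patients have 5.95 months, a share of about 48% lifts the mixed median from 3.7 to 4.6 months.

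**The case against.** **The intended regimen is clear.** The title, the primary objective and section 5.1 describe doxorubicin with dexrazoxane only. The team also amended the protocol to let in olaratumab, which suggests that it did not regard add-ons as already open. This stands as evidence of intent. But none of those passages works as an entry limit, and the amendment also shows that patients on an add-on could enter the same primary test.

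**The 7.4-month figure is the favourable half of section 1.2.** The same section reports another randomised trial, including doxorubicin plus ifosfamide, in which combinations did not significantly improve PFS. The reference list describes the 7.4-month regimen as intensified doxorubicin plus ifosfamide, so its ratio need not carry over to other drugs. For olaratumab, section 1.7 says that benefit was not confirmed. This stands. A reader might infer that any add-on drug distorts the test; the documents do not support that.

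**The share is unknown and may be zero.** This also stands. No document shows a patient planned for doxorubicin plus ifosfamide.

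**Section 1.4 does not say that the trial is designed to avoid add-ons.** Correct. It concerns breast cancer regimens and implies that the authors did not expect this confounder in routine sarcoma care.

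**A share of 34% could be said to turn 3.7 months into 4.6.** That holds only if combination patients keep the full 7.4 months while single-agent patients alone lose 20%. If the loss applies to everyone, the share is about 48%.

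**Conclusion.** The mismatch is real. The benchmark and hypothesis concern doxorubicin alone, while the entry, exclusion and concomitant-therapy rules admit patients on other approved combinations, and the primary analysis pools them. An effective add-on would bias the test toward non-inferiority.

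The size is conditional. At the largest ratio in the documents, shares of 10% to 30% give false non-inferiority of 0.11 to 0.34 by log-rank and about 0.05 to 0.12 by the Kaplan-Meier lower limit. With an ineffective add-on there is no inflation. These figures assume exponential PFS, complete follow-up, a true single-agent median at the margin, and shares that have no source in the documents.

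A reader might conclude that the trial's result is already biased or that olaratumab has inflated it. The documents support neither; they show only that the plan as written does not prevent the problem or measure it. The severity is should-fix.

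**What to change.** 1. Reconcile inclusion 3 and section 5.1 with the single-agent comparator in 14.3.1, so that the protocol states which accompanying regimens the primary conclusion covers.
2. Record the anticancer regimen planned at registration and any concurrent anticancer drugs. Section 11.0 already lists a Treatment Form for every cycle. Its fields are not shown, so first check whether it captures this.
3. In 14.2, pre-specify the comparison with 4.6 and 3.7 months in patients whose regimen planned at registration was doxorubicin plus dexrazoxane with no other anticancer drug. Defining the set at registration avoids selection on later events.
4. Report that comparison beside the full intention-to-treat result, and require it to support the same conclusion before claiming non-inferiority to doxorubicin alone.
5. Report patients on other regimens, including olaratumab, separately.

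**Cost.** A few sentences, possibly one form field, and chart abstraction for patients already enrolled. The matched set will be smaller and less precise. The loss could be more than a few patients, because the amendments that allowed and removed olaratumab are dated 10/17/16 and 02/04/19. That is why the intention-to-treat result should be kept and not replaced. If no patient had an add-on, the two analyses coincide and the record shows it.
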